AE	Adverse Event
AR	Adverse Reaction
CA	Competent Authority
CCMO	Central Committee on Research Involving Human Subjects; in Dutch: Centrale Commissie Mensgebonden Onderzoek
CV	Curriculum Vitae
DSMB	Data Safety Monitoring Board
EU	European Union
EudraCT	European drug regulatory affairs Clinical Trials
GCP	Good Clinical Practice
GDPR	General Data Protection Regulation; in Dutch: Algemene Verordening Gegevensbescherming (AVG)
IB	Investigator's Brochure
IC	Informed Consent
IMP	Investigational Medicinal Product
IMPD	Investigational Medicinal Product Dossier
METC	Medical research ethics committee (MREC); in Dutch: medisch-ethische toetsingscommissie (METC)
(S)AE	(Serious) Adverse Event
SPC	Summary of Product Characteristics; in Dutch: officiële productinformatie IB1-tekst
Sponsor	The sponsor is the party that commissions the organisation or performance of the research, for example a pharmaceutical company, academic hospital, scientific organisation or investigator. A party that provides funding for a study but does not commission it is not regarded as the sponsor, but referred to as a subsidising party.
SUSAR	Suspected Unexpected Serious Adverse Reaction
UAVG	Dutch Act on Implementation of the General Data Protection Regulation; in Dutch: Uitvoeringswet AVG
WMO	Medical Research Involving Human Subjects Act; in Dutch: Wet Medisch-wetenschappelijk Onderzoek met Mensen

SUMMARY

Rationale: Kidney transplantation is the standard treatment for end stage renal disease (ESRD). Patients with aortoiliac stenosis are often ineligible for kidney transplantation due to the high risk of vascular complications.

Objective: To assess the impact of pre-transplant aorto-iliac stenosis on short and long term outcomes of kidney transplant patients.

Study design: Single-centre retrospective cohort study

Study population: Patients who underwent kidney transplantation in Erasmus MC between January 2010 and December 2020.

Intervention (if applicable): NA

Main study parameters/endpoints: Primary outcome measures are patient survival and death-censored graft survival and secondary outcome measures are renal function (such as eGFR) and the incidence rate of vascular complications.

Nature and extent of the burden and risks associated with participation, benefit and group relatedness: This is a retrospective cohort study and no additional burden or risks will be applied to the patients.

1. INTRODUCTION AND RATIONALE

Kidney transplantation has been recognized as the paramount therapy for end stage renal disease. It increases the quality of life and survival rate of patients when compared with long-term hemodialysis(1). For patients who are ineligible for kidney transplantation, peritoneal dialysis or hemodialysis is the only alternative option. According to the annual data report of 2016 from the United States Renal Data System, the overall 5 year survival of hemodialysis patients is 41,6% and for peritoneal dialysis 59,4% (2). In comparison to those survival rates, the survival rate in patients receiving a deceased-donor kidney transplant was 75,7% and for patients receiving a living-donor kidney transplant 84,6%(2). Therefore, kidney transplantation should be the first choice of therapy in patients with end stage renal disease. There is little known about the proportion of renal transplant candidates who are considered ineligible by the transplant center. Kianda et al. investigated that 8% of the referred patients were considered ineligible and he described in 44% of the patients aorto-iliac atherosclerosis as the only reason (3). Other less frequent reasons for ineligibility in this study were severe ischemic heart disease, advanced age, metastatic neoplasia and severe impairment of general status or a combination of these factors. This shows that aorto-iliac atherosclerosis is the most frequent reason why patients are considered ineligible for kidney transplantation.

There are a number of concerns when considering kidney transplantation in patients with aortoiliac atherosclerosis. At first, it may complicate a vascular anastomosis between donor renal artery and recipient iliac artery during transplantation, sometimes even requiring a vascular procedure. Secondly, 'steal syndrome' can occur whereby the transplanted organ results in redirection of blood flow from an already vulnerable limb leading to distal ischemia. This syndrome has been showed in children undergoing renal transplantation(4). However, Northcutt et al. investigated this syndrome in adults and he did not show significantly deterioration of ischemia(5). The third concern is the physiologic impact of a complex operation on these critically ill patients(6, 7). Finally, a recent study concluded that aortic calcification index can progress after transplantation and represent a post-transplant cardiovascular event risk factor(8). As a result of these concerns, aorto-iliac atherosclerosis is a relative contraindication for kidney transplantation.

Over the years, a few case series and case reports have been published about aorto-iliac calcifications in renal transplant patients requiring a vascular procedure(6, 7, 9-18). Those case series report very successful short term survival and graft function. However, the impact of aorto-iliac calcifications on long term survival in kidney transplant patients remains unclear. Because of the poor survival of patients requiring dialysis, broader patient selection for kidney transplantation is desirable. The present study aims to assess the impact of pre-transplant aorto-iliac stenosis on short and long term outcomes of the kidney transplant patients.

2. OBJECTIVES

Primary Objective: This study aims to assess the impact of pre-transplant aorto-iliac stenosis on short and long term outcomes of kidney transplant patients.

3. STUDY DESIGN

This single-center retrospective study includes all kidney transplant patients who underwent kidney transplantation in Erasmus MC between 2010 and 2020. Data of patient characteristics, operation details and long-term outcomes will be collected. All patients will be divided into non-stenosis group and stenosis group based on the existence of pre-transplant aortoiliac stenosis. Propensity score matching will be used to make the baseline characteristics comparable between two groups. Patient survival, graft survival and long-term renal function of the two groups will be compared to indicate if the aortoiliac stenosis has an impact on the survival of transplant patients.

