4. STUDY POPULATION

4.1 Population (base)

The research population are patients (n= ~2000) who underwent kidney transplantation in Erasmus MC between Jan 2010 and December 2020. Based on the pre-transplant existence of aortoiliac stenosis, all patients will be divided into non-stenosis group (n=~1800) and stenosis group (n=~120).

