4.4 Sample size calculation

Sample size calculation is performed by G*Power for future use of t test. Both the accepted false positive and negative rate is 5%. The results indicate the sample size should be at least 105 in each group to reach a reliable answer, which is feasible based on the current patient population.

The protocol of power analyses are as follows:

Analysis: A priori: Compute required sample size

Input:	Tail(s)	=	Two
	Effect size d	=	0,5
	α err prob	=	0,05
	Power (1- β err prob)	=	0,95
	Allocation ratio N2/N1	=	1
Output:	Noncentrality parameter δ	=	3,6228442
	Critical t	=	1,9714347
	Df	=	208
	Sample size group 1	=	105
	Sample size group 2	=	105
	Total sample size	=	210
	Actual power	=	0,9501287

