8. METHODS

8.1 Study parameters/endpoints

8.1.1 Main study parameter/endpoint

Primary outcome measures are patient survival and death-censored graft survival.

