10. STATISTICAL ANALYSIS

Patient survival, death-censored graft survival and eGFR will be reported as mean \pm standard deviation (SD) if normally distributed or median with interquartile range (IQR) if data is skewed. Categorical variables such as the incidence rate of vascular complications will be described as numbers and percentages. Continuous variables will be compared using student's t-test or Mann–Whitney U test. Categorical variables will be compared using χ^2 test or Fisher's exact test. Kaplan-Meier curves and log-rank test will be used to compare patient and graft survival. The data will be analyzed in SPSS. A p-value of < 0.05 is considered statistically significant.

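### The matching ratio is not set and no hazard ratio or interval is planned; matching up to 1:4 with a weighted Cox model would cut the variance of the log hazard ratio by up to about 37.5% against 1:1 at equal event risks, and by less if overlap is poor

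*Combined protocol and SAP*

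**What the plan says.** Section 3 (Study design) is the only place that mentions matching: "Propensity score matching will be used to make the baseline characteristics comparable between two groups". No ratio, caliper, replacement rule, covariate list or rule for unmatched patients follows. The same section covers all patients transplanted in the period: "Data of patient characteristics, operation details and long-term outcomes will be collected".

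Section 4.1 gives the group sizes: "all patients will be divided into non-stenosis group (n=~1800) and stenosis group (n=~120"), a ratio of about 15 to 1.

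Section 4.4 sizes the study with a two-sided t-test: "The results indicate the sample size should be at least 105 in each group to reach a reliable answer". Its input "Allocation ratio N2/N1" is set to 1. This is not presented as a matching rule.

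Section 8.1.1 names the primary endpoints: "Primary outcome measures are patient survival and death-censored graft survival". For these, Section 10 plans: "Kaplan-Meier curves and log-rank test will be used to compare patient and graft survival". It names no Cox model, hazard ratio, confidence interval or method for matched sets. It also fixes the software: "The data will be analyzed in SPSS".

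**The concern.** There are two linked gaps.

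- **No effect estimate.** The objective in Section 2 is to assess the impact of stenosis. A log-rank p-value judged at 0.05 gives neither the size of that impact nor its uncertainty. If the result is non-significant, a reader cannot tell no important harm from too few events. Section 1 argues for broader patient selection, and that distinction is what the argument needs.
- **No matching rule.** The outcomes of this retrospective cohort already exist, so a ratio and caliper left open can be chosen after results are seen. If the ratio of 1 in Section 4.4 is carried over by default, most of the roughly 1,800 comparators are discarded and the interval is wider than overlap requires.

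**Working it through.** **The plan's own figure.** With d = 0.5, two-sided alpha 0.05 and 105 per group, the noncentrality is 0.5 × √(105/2) = 3.6228, the critical t on 208 degrees of freedom is 1.9714 and power is 0.9501. Section 4.4 reproduces exactly. It concerns a difference in means, so it says nothing about the precision of a hazard ratio.

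**Relative gain at equal event risks.** Var(log HR) ≈ 1/d1 + 1/d0, where d1 and d0 are the events in the stenosis and comparator groups. With all 120 stenosis patients matched 1:k, the variance is proportional to 1 + 1/k. The reduction against 1:1 is 1 − (1 + 1/k)/2.

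| Ratio | Comparators | Reduction in variance |
|---|---|---|
| 1:2 | 240 | 25% |
| 1:3 | 360 | 33.3% |
| 1:4 | 480 | 37.5% |
| 1:5 | 600 | 40% |

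Little is gained beyond four. At 1:4 the standard error (SE) is multiplied by √0.625 = 0.79, so it falls by about 21%.

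**Incomplete matching.** If comparators carry weight w = 1/m in a set with m matches, the effective comparator size is (Σw)²/Σw². With 60, 30 and 30 sets having 4, 2 and 1 matches, it is 120²/(15 + 15 + 30) = 240. With 30, 30 and 60 such sets it is 120²/(7.5 + 15 + 60) = 174.5. At an effective size of 150 and equal risks, the reduction is 1 − (1/120 + 1/150)/(2/120) = 10%.

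**Absolute illustration.** The documents give no expected hazard ratio, cohort event rate or follow-up length, so these are assumed: HR 1.5, 5-year comparator survival 80%, exponential hazards, follow-up uniform over 1 to 12 years.

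- Hazards: λ0 = −ln(0.80)/5 = 0.0446 and λ1 = 1.5 × λ0 = 0.0669 per year.
- Event probability: P = 1 − (e^(−λ) − e^(−12λ))/(11λ), giving P0 = 0.244 and P1 = 0.338.
- Events at 1:1: d1 = 120 × 0.338 = 40.6 and d0 = 120 × 0.244 = 29.3.
- SE = √(1/d1 + 1/d0); power = Φ(ln 1.5/SE − 1.96).

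| Effective comparators | SE | 95% CI around 1.5 | Power | Reduction in variance |
|---|---|---|---|---|
| 120 (1:1) | 0.242 | 0.93-2.41 | 39% | – |
| 150 | 0.228 | 0.96-2.34 | 43% | 11.6% |
| 240 | 0.204 | 1.01-2.24 | 51% | 29.0% |
| 480 (complete 1:4) | 0.182 | 1.05-2.14 | 60% | 43.5% |

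**Varying the assumptions.**

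- With the survival rates quoted in Section 1 (84.6% and 75.7%) in place of 80%, the complete 1:4 reduction is 44% and 43%.
- For death-censored graft survival, assumed 90% at 5 years, the SE falls from 0.335 to 0.250 and power rises from 23% to 37%.
- If events are rarer with stenosis (HR 0.67, 80% survival), the reduction is about 31%.
- If hard-to-match patients are at higher risk (assumed 5-year survival 87%, 80% and 65% in sets with 4, 2 and 1 matches), the comparator term becomes Σ(kP/m)/(ΣkP)², with k the number of sets of each kind. The reductions for the two incomplete patterns fall from 29% to 22% and from 18% to 11%.

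**Check by simulation.** The formula ignores correlation within matched sets and the poorer quality of later matches. A simulation with both used 1,920 patients, 6.25% with stenosis, five normal covariates, HR 1.5, greedy matching with a 0.2 SD caliper, 1/m weights and clustered standard errors. Over 400 runs per setting, the mean estimated variance was 28% lower with poor overlap and 43% lower with good overlap (31% to 46% in empirical variance). The mean residual standardised difference of the risk score was at most 0.05 for 1:4 and 0.02 for 1:1. The share of unmatched stenosis patients ran from 0 to 25% and was the same for both ratios. This rests on one assumed covariate structure.

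**The case against.** The strongest case on the other side does not dispute the arithmetic.

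- **The baseline is not in the plan.** Section 4.4 gives a minimum per group, not a cap, and nothing excludes 1:k matching. If the analysts already intend several matches, the saving is nil. This stands, so the percentage is conditional on 1:1 being used. The absence of a rule is a defect either way.
- **Kaplan-Meier curves do show a difference.** They do, and a reader can see its rough size. What is missing is a stated contrast with a confidence interval. That gap needs no percentage to support it.
- **Variance flatters the gain.** The 37.5% is about 21% in SE, and in the illustration power stays low even at 1:4 (60% and 37%). The change improves precision; it does not make the study adequately powered.
- **Poor overlap is plausible.** Section 1 calls aorto-iliac disease a relative contraindication, so transplanted patients with it may differ markedly from the rest. The gain could then be 10-22%. If 25% of stenosis patients were unmatched, about 90 of 120 would remain, below the 105 in Section 4.4. No choice of ratio cures that.
- **Other methods could serve.** Weighting or covariate adjustment on all of about 1,920 patients would also use the data, and one hazard ratio presumes proportional hazards. Both are fair. A proportional-hazards check is a useful addition, but its absence does not make the proposal unsound.

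**Conclusion.** The concern holds. Section 3 sets no matching ratio or caliper, and Section 10 gives no effect estimate or interval for either primary outcome. Against 1:1, complete 1:4 matching lowers the variance of the log hazard ratio by 37.5% at equal event risks with all 120 stenosis patients matched. The gain is about 43% if the hazard ratio is 1.5, and 10-12% if overlap holds the effective comparator size to 150. These are scenarios, not bounds. The 1:1 baseline is inferred from Section 4.4, and every absolute SE and power figure rests on assumed event rates and follow-up. The study could run as written, so this is a change that should be made rather than a fatal flaw. Confidence is medium, because the degree of overlap is unknown.

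**What to change.** **Section 3.** State that each stenosis patient will be matched without replacement to up to four non-stenosis patients, within a caliper fixed before outcomes are examined (for example 0.2 SD of the logit of the propensity score). Name the pre-transplant covariates in the propensity model, including transplant year and donor type. Check balance by standardised mean differences. Count and describe unmatched stenosis patients, and report the number of matches per patient.

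**Section 10.** For both primary outcomes, report a Cox hazard ratio with 95% confidence interval beside the Kaplan-Meier curves. Weight each comparator by 1/(number of comparators in its set) and use robust standard errors clustered on matched set. Make 1:1 matching a sensitivity analysis. It would also help to add a proportional-hazards check, with a survival difference at a prespecified time if the assumption fails. Amend the software statement if another package is needed.

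**Cost.** Wording in two sections, a little extra programming and possibly the software amendment. No new patients or data items are needed, because Section 3 already covers the whole cohort. The drawback is that later matches may be less close than the first; the caliper, the balance check and the 1:1 sensitivity analysis limit and reveal this.

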4.2 Inclusion criteria

Patients who underwent kidney transplantation in Erasmus MC between Jan 2010 and December 2020 will be included in the study.

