4.3 Exclusion criteria

Patients under 18 years old and who underwent combined kidney and liver transplantation will be excluded from the study.

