11.2 Recruitment and consent

Gathering the express consent of test subjects is only possible by exerting disproportionate effort or would lead to unacceptable selection bias. All allogeneic kidney transplantation recipients from 2010 to 2020 are included in this study. The study population concerns patients that have been treated 10 years ago; A substantial amount of the study population is expected to have passed away and/or has no records available about current whereabouts. Asking express consent could result in an unacceptable selection bias and therefore produce unreliable data. Recovering addresses would involve a disproportionate effort for gathering the express consent of test subjects. The Form exception informed consent is attached as a separate document.

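### Matching on undefined baseline characteristics is the only control of confounding, and neither donor type nor transplant date is named, although transplants span 11 years and the plan quotes different survival by donor type

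*Combined protocol and SAP*

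**What the plan says.** Section 3 gives the whole matching specification: "Propensity score matching will be used to make the baseline characteristics comparable between two groups". No section lists the covariates, matching ratio, caliper, exact-match factors or a balance criterion. The same section names the data: "Data of patient characteristics, operation details and long-term outcomes will be collected". Donor data are not mentioned.

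The cohort is wide. Section 4.2 states: "Patients who underwent kidney transplantation in Erasmus MC between Jan 2010 and December 2020 will be included in the study". Section 11.2 adds: "All allogeneic kidney transplantation recipients from 2010 to 2020 are included in this study". Section 4.3 excludes only minors and combined kidney-liver transplants, so both donor types appear eligible. On group sizes, section 4.1 says "all patients will be divided into non-stenosis group (n=~1800) and stenosis group (n=~120".

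Section 1 quotes registry survival after transplantation by donor source, in per cent: "deceased-donor kidney transplant was 75,7% and for patients receiving a living-donor kidney transplant 84,6".

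Section 10 compares patient and graft survival by Kaplan-Meier curves and a log-rank test, with no stratification and no regression model. It also summarises both survival outcomes as mean with SD or median with IQR, and assigns continuous variables to a t-test or Mann-Whitney test. Section 10.1 runs follow-up to death, graft failure or last follow-up, with no cut-off date or common horizon. Sections 8.1.2 and 10.2 give no time point for eGFR.

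**The concern.** The study wants to attribute differences in outcome to stenosis. Nothing after the matching step can correct an imbalance that matching leaves behind, so everything depends on which variables enter it, and that is not stated.

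Two variables stand out. Donor type is the one prognostic split among transplanted patients for which the plan gives figures. Transplant date matters because section 1 calls aorto-iliac atherosclerosis a relative contraindication and wants broader selection. Acceptance of such patients, and the care around them, may therefore have changed over 11 years. If either differs between the matched groups, part of the difference in survival belongs to donor or era and would be reported as an effect of stenosis.

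Date also fixes potential follow-up. That matters wherever survival time or eGFR is compared without regard to how long each patient could have been observed.

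**Working it through.** **Plan's own figure.** Section 4.4: two-sided t-test, d = 0.5, alpha 0.05, power 0.95, 1:1. With n = 105 per group, the noncentrality is 0.5 × √(105/2) = 3.6228, df = 208, critical t = 1.9714 and power = 0.9501. This agrees with the plan. The figure has no input for matching or donor type. It is used here only as the plan's minimum group size.

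**Donor type.** Inputs: 75.7% and 84.6% (section 1), read as 5-year survival because the sentence before gives 5-year figures for dialysis.

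- Hazard ratio, deceased against living: ln(0.757)/ln(0.846) = 0.2784/0.1672 = 1.66.
- Assume no stenosis effect and deceased-donor share p. Five-year survival is then S = 0.757p + 0.846(1 − p).
- Non-stenosis group, p = 40% (assumed): S = 0.8104.

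| Assumed deceased-donor share, stenosis vs non-stenosis | S, stenosis | Difference, points | False hazard ratio, ln(S, stenosis)/ln(0.8104) |
|---|---|---|---|
| 50% vs 40% | 0.8015 | 0.9 | 1.05 |
| 60% vs 40% | 0.7926 | 1.8 | 1.11 |
| 70% vs 40% | 0.7837 | 2.7 | 1.16 |
| 80% vs 40% | 0.7748 | 3.6 | 1.21 |

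If the mix leans the other way, the false effect reverses.

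**Effect on the test.** Simulation with 120 per group, 4,000 runs, exponential survival at the rates above, no stenosis effect, even accrual over 11 years and data cut-off 12 years after January 2010 (assumed). The log-rank test rejects in 4.6% with equal donor mix and dates, 8.8% at 70% vs 40%, and 16.0% at 80% vs 30%.

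**Follow-up alone.** Same simulation, equal donor mix, stenosis patients transplanted later on average.

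| Mean shift in date | Log-rank rejects | t-test on observed time rejects |
|---|---|---|
| none | 4.6% | 5.0% |
| 1 year | 5.1% | 47.7% |
| 2 years | 5.2% | 98.4% |

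The log-rank test stays at its nominal level. The t-test on observed time does not, because it reads shorter observation as shorter survival. Unequal dates would likewise put eGFR at different times since transplantation if, for example, the last available value were used.

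**Numbers at late times.** Under the same accrual and cut-off, potential follow-up runs from 1 to 12 years: (5 − 1)/11 = 36% of patients have under 5 years and (12 − 10)/11 = 18% have 10 or more. This concerns precision late in the curves. It is not a bias.

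**Room for closer matching.** 1,800/120 = 15 controls per stenosis patient, or 1,800/11 = 164 controls against 120/11 = 11 cases per year. At 70% vs 40% the deceased-donor stratum has 0.4 × 1,800 = 720 controls for 0.7 × 120 = 84 cases, 8.6 each. The living-donor stratum has 1,080 controls for 36 cases, 30 each. A ±1-year band is two years wide, so it holds about 720 × 2/11 = 131 deceased-donor controls, and half that at the ends of the window. The margin on the plan's own target is 120 − 105 = 15 cases.

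**The case against.** A reader might infer that the plan leaves donor type and era out of the match. The documents do not say so. Both are known at transplantation and are ordinary candidates for baseline characteristics, and operation details could include donor type. Transplant date must be collected anyway, since it selects patients (section 4.2) and starts the survival clock (section 10.1). What can be shown is that neither is committed to.

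A reader might also infer that unequal follow-up biases the primary survival comparison. It does not under non-informative censoring, as the simulation confirms. The harm is confined to survival time treated as an ordinary continuous variable and to eGFR. Section 10 does not state outright that survival time will be t-tested, but its wording allows it, and section 4.4 sizes the study for a t-test.

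Nor does each pair have to agree on date and donor. The planned log-rank test is unpaired, so balance between groups is enough. A 2020 case paired with a 2010 control is no bias if the date distributions agree. Exact matching is therefore one sound method and not the only one.

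The size rests on assumption. The survival figures are from a US registry, not this centre, and are crude: part of the 1.66 may reflect recipient factors that matching would balance. The donor mix by stenosis status is not given.

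Finally, if stenosis influences which donor is offered, matching on donor type removes that part of its impact. This stands, and it must be stated as part of what is estimated.

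After all this, the core remains: the sole protection against confounding is undefined on two factors that matter.

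**Conclusion.** The point holds as a gap in specification with modest consequences. If donor type stays unbalanced, the unadjusted log-rank comparison of patient survival can show a false stenosis hazard ratio of about 1.11 to 1.21, for assumed deceased-donor shares of 60% to 80% against 40%. Its direction is unknown. This rests on the registry figures being 5-year survival and applying to this cohort. The documents give no corresponding figure for death-censored graft survival or for an era effect on the hazard, so neither can be sized.

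Unequal follow-up is a separate and narrower matter: harmless to the log-rank test, serious for a t-test on observed survival time. The documents do not support saying that the matched groups will differ in donor or era, or that the primary comparison is invalid. It is a change worth making because it is cheap and the control pool allows it.

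**What to change.** In section 3:

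- Add donor type (living or deceased) to the data collected.
- Match exactly on donor type and within a band of transplant date (for example ±1 year), then on the propensity score. Putting donor type and date in the score, with a stated balance check on both, is an acceptable alternative.
- Keep several controls per case where they fit. If the number varies between cases, weight the controls or stratify the analysis by matched set. Otherwise the differing supply (8.6 against 30 per case in the example) would bring the donor imbalance back.
- If donor type is matched, state that the estimate is the effect of stenosis at a given donor type.

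In section 10:

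- Compare and summarise survival only with censoring-aware methods. Drop the mean or median of observed time.
- Set a data cut-off date and fixed time points for eGFR.
- Report unmatched stenosis patients, and numbers at risk by group at the long-term time points.

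The cost is wording and one variable that should be in the transplant record. The downside is that a few stenosis patients may find no match. About 15 can be lost before the group falls below the planned 105. The overall 15:1 ratio does not guarantee overlap on the remaining covariates, so the actual loss should be counted before the matching rule is fixed and before outcomes are examined.

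### Propensity score matching is the only control of confounding; the plan sets no balance criterion and compares outcomes unadjusted, so any imbalance left by matching is attributed to stenosis

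*Combined protocol and SAP*

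**What the plan says.** Section 3 (Study design) divides the transplant cohort by pre-transplant aorto-iliac stenosis and gives one sentence on confounding: "Propensity score matching will be used to make the baseline characteristics comparable between two groups". It then says that patient survival, graft survival and renal function will be compared to show whether stenosis affects survival. It does not state the covariates in the score, the matching ratio, a caliper, a balance measure or a balance limit.

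Section 10 (Statistical analysis) lists the comparison methods:

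- "Continuous variables will be compared using student's t-test or Mann–Whitney U test", without saying whether this covers baseline variables, outcomes or both.
- A chi-square or Fisher test for categorical variables, in the same general terms.
- For the primary endpoints: "Kaplan-Meier curves and log-rank test will be used to compare patient and graft survival".
- One threshold for all of these: "A p-value of < 0.05 is considered statistically significant".

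Sections 10.1 and 10.2 define the outcomes and the eGFR source only. Neither document section mentions standardised differences, a regression model, a stratified or paired analysis, or adjustment after matching.

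**The concern.** The study asks a causal question with observational data. Section 1 describes aorto-iliac atherosclerosis as a relative contraindication to transplantation, so the two groups can be expected to differ in prognosis for reasons other than the stenosis. All of that difference has to be removed by matching, because nothing later in the analysis removes any of it.

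Two things can go wrong. Chance imbalance can remain in a matched set of about 100 pairs. More seriously, a score that omits a needed term (for example, a curved effect of age) can leave a systematic difference that a comparison of means does not reveal. Both pass directly into the log-rank test and the eGFR comparison. An apparent harm of stenosis produced this way would argue against the broader patient selection that Section 1 calls desirable.

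**Working it through.** **Inputs from the documents.** Section 4.4: two-sided test, alpha 0.05, power 0.95, d = 0.5, allocation ratio 1, critical t 1.9714 on 208 df, 105 per group. Section 4.1: about 120 stenosis and about 1800 non-stenosis patients, so at most about 120 pairs under 1:1 matching.

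**Inputs assumed here.** Age SD 13 years; 5% higher hazard of death per year of age (range 3% to 7%); 1:1 matching. The ratio of 1 in Section 4.4 is a sample-size input, and no matching ratio is stated.

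**1. The plan's own figure.** The noncentrality parameter is 0.5 × sqrt(105/2) = 3.6228. With critical t 1.9714 the noncentral t distribution gives power 0.9501 at 105 per group and 0.9483 at 104. The stated 105 per group reproduces.

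**2. What a significance test of balance could miss.** The largest standardised difference that still gives p ≥ 0.05 is t(0.975, 2n−2) × sqrt(2/n).

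- n = 105: 1.9714 × sqrt(2/105) = 0.272 SD
- n = 120: 0.254 SD
- n = 80 (assumed, if fewer pairs are found): 0.312 SD
- 120 stenosis patients matched 1:2 to 1:5: 0.22 to 0.20 SD

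At 105 per group, a true imbalance of 0.10, 0.20 or 0.25 SD is flagged with probability 0.11, 0.30 or 0.44. For a binary covariate with assumed reference prevalence of 20% to 50%, the uncorrected chi-square test misses differences of about 11 to 13 percentage points.

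**3. What residual is realistic.** A simulation used 1920 patients, eight normal covariates, a correctly specified score and 1:1 matching with a caliper of 0.2 SD of the logit. Over 300 runs it gave about 96 pairs on average. The strongest, age-like covariate had a mean standardised difference of 0.001 and a 95th percentile of 0.14, and exceeded 0.2 in no run. So 0.14 SD is already towards the upper end when the score is right.

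**4. Carry-over to the hazard ratio.** Spurious hazard ratio = (1 + hazard increase per year)^(standardised difference × SD).

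- 0.14 SD: 0.14 × 13 = 1.8 years; 1.05^1.8 = 1.09
- 0.27 SD: 0.27 × 13 = 3.5 years; 1.05^3.5 = 1.19; 1.03^3.5 = 1.11; 1.07^3.5 = 1.27

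The log hazard ratio is proportional to the assumed SD, so a different SD scales these results directly.

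**5. Misspecified score.** In a separate simulation (500 runs) the score omitted one curved, age-type term. The mean log hazard ratio in the matched sample was 0.089 unadjusted (exp(0.089) = 1.09), 0.083 with linear adjustment, and −0.003 (1.00) when the curved term was in the outcome model. Adjustment removed the bias only when it had the right form.

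**The case against.** **The balance check is not in the plan.** A reader might infer that non-significant tests will be taken as proof of comparability. The documents do not say so. Section 10 names the outcomes and then speaks of continuous and categorical variables in general. What can be said is that no balance criterion exists and that significance tests are the only comparison tools listed. This stands, and the 0.27 SD figure is conditional on it.

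**A hazard ratio of 1.19 is not the likely bias.** A reader might take the detection limit as the expected imbalance. It would require age, an obvious matching variable, to stay 0.27 SD apart with about 1800 controls available. The simulations point to about 1.09. This also stands.

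**Frequent differences above 0.1 do not show harm.** In simulated matched sets with eight covariates, about 90% had some standardised difference above 0.1, while t-tests flagged any covariate in only 1% to 2%. A reader might infer that the tests hide damaging imbalance. But under pure randomisation with 105 per group the differences have SD sqrt(2/105) = 0.138, so each exceeds 0.1 with probability 0.47, and at least one of eight independent ones does with probability 1 − 0.53^8, about 99%. Such residuals centre on zero and favour neither direction; only misspecification gives a systematic bias.

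**Adjustment is no guarantee.** Linear adjustment barely helped in step 5, and adjusting for the score alone would carry over the same misspecification. This limits the remedy but does not justify having none.

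What the objections leave untouched is the central gap: no balance criterion, and no adjustment after matching.

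**Conclusion.** The concern holds as a gap in the analysis plan. Matching is the sole control of confounding, nothing in the plan would show whether it succeeded, and the unadjusted comparisons assign any remainder to stenosis. A plausible size is a spurious hazard ratio of about 1.09, resting on a 0.14 SD residual in age, an SD of 13 years and 5% higher hazard per year. The upper bound is 1.19 (1.11 to 1.27 for 3% to 7% per year), which needs 1:1 matching, 105 per group and an imbalance right at the limit of what a t-test would pass. The documents support neither a claim that balance will be declared from p-values nor a claim that a large bias is expected. The plan should be changed because the better method is available at little cost, not because the planned result is bound to be wrong.

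**What to change.** In Section 10:

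1. **Balance.** Report standardised mean differences and variance ratios before and after matching, without p-values. Refine the score (for example with curved terms for age) before outcome data are merged. Use 0.1 as a target, not as a condition that every covariate must meet: that limit is a convention, is not in the documents, and at this sample size could lead to an endless search.
2. **Outcome models.** For patient survival and death-censored graft survival, make the primary comparison a Cox model on the matched sample, with robust standard errors clustered on matched pair. Adjust for a short, pre-specified list of the strongest prognostic covariates in the score, with age as a curved term. Use a linear model adjusted in the same way for eGFR. Keep the Kaplan-Meier curves and the log-rank test as unadjusted display.

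The cost is about a paragraph of text and slightly more analysis, using covariates that the score needs anyway. The number of graft losses limits how many covariates the second model can carry, so the list must be short and fixed in advance.
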